During our conversation, I'll ask you questions about yourself, your visit companion, and your interactions with your doctor. Your "visit companion" is the family member or friend who comes with you to your health appointments. Your "doctor" is the doctor, nurse practitioner, or other health care provider who you usually see during your visit.

After completing the prompt and if the participant is able to conduct their data collection at that time, the RA/SC will collect their data either by using one of the following: 1) paper data collection materials; 2) the iPad REDCap application; or 3) by computer using the REDCap online data capture system. Regardless of the way in which the data is collected, each data collection will be administered uniformly to all participants.

Below are the **BASELINE QUESTIONNAIRES** with their respective variables for analysis for patients

List of measures included in this questionnaire:

1. Relationship with companion
2. Companion involvement
3. Closeness with companion
4. Health literacy
5. Knowledge of heart failure+
6. Self-care behaviors
7. Self-efficacy related to self-care
8. Perceived health status
9. Heart failure symptom severity
10. Communication with provider
11. Perceived efficacy in interactions with doctor
12. Perceived social support
13. Demographic/background questions

*Note that the Baseline Questionnaires **for companions** includes the following measures, which parallel the patient questionnaires:

List of measures included in this questionnaire:

1. Relationship with patient
2. Companion involvement
3. Closeness with patient
4. Knowledge of heart failure
5. Caregiver care behaviors
6. Self-efficacy related to patient care
7. Perceived efficacy in interactions with doctor
8. Demographics
9. Health literacy

Companion for visit with doctor

1. **Will you have a companion, such as a family member or friend, come with you to visit your doctor during this study? Variable name: accompanied**

- a. Yes
- b. No

IF NO:

- 2. Does someone usually go with you to your medical appointments? **Variable name: usual_accomp**
 - a. Yes
 - b. No

Relationship with Companion

[IF PARTICIPANT WILL NOT HAVE A COMPANION COME WITH THEM TO THEIR APPT, ASK ABOUT THE PERSON WHO USUALLY GOES WITH THEM. IF PARTICIPANT DOES NOT USUALLY HAVE A COMPANION COME WITH THEM TO THEIR APPT, SKIP AHEAD TO HEALTH LITERACY.]

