4.2 Follow-up procedures (by visits)

2 DAY & 1 MONTH FOLLOW UP CALL ADMINISTRATION PROTOCOL

Hello, _____. This is [NAME] calling from UNC Health Care. I'm calling about the Partners in Heart Health Research Study that you are participating in. Thanks again for participating in our study.

I'd like to ask you a few questions about your most recent appointment [interviewer to specify when the appointment was- e.g. 2 days ago]. Our conversation should take about 15 minutes. Is this a good time to talk?

Yes → [Continue]

No → [Reschedule interview for next available time- preferably within the same week]

During our conversation, I'll ask you questions about yourself, your visit companion, and your interactions with your provider. Your "visit companion" is the family member or friend that came with you to your appointment. Your provider is the doctor or nurse practitioner you saw during your visit.

2-Day Follow-Up Measures

1. Prompt List Acceptability
2. Satisfaction with visit
3. Perceptions of provider communication
4. Patient communication
5. Perceived efficacy in interactions with doctor
6. Self-efficacy related to self-care

The following protocol is for the administration of the 2 Day Follow Up and the 1 Month Follow Up Calls for each study participant.

Hello, _____. This is [NAME] calling from UNC Health Care. I'm calling about the Heart Failure Study that you joined earlier this year. My records show that your family member or friend had an appointment with their healthcare team 2-3 days ago. Is that right?

Yes → [Continue]

No → [Clarify appointment date and reschedule interview accordingly]

As part of the study, I'd like to ask you a few questions about your family member or friend's appointment. Our conversation should take about 15 minutes. Is this a good time to talk?

Yes → [Continue]

No → [Reschedule interview for next available time]

During our conversation, I'll ask you questions about yourself, your family member or friend who has heart failure, and your interactions with the doctor who treats your family member or friend's heart failure. We will use "doctor" to refer to the doctor, nurse practitioner, or physician assistant who your family member or friend usually sees during medical appointments.

[*Note that the 2-day follow-up questionnaires **for companions** includes the same measures, which parallel the patient questionnaires].

Prompt List Acceptability

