3. I went into great detail about my medical symptoms [detailed_sxs2](#)

Strongly disagree									Strongly agree
0	1	2	3	4	5	6	7	8	9

4. I asked the doctor to explain the treatment or procedure in greater detail [explain_tx2](#)

Strongly disagree									Strongly agree
0	1	2	3	4	5	6	7	8	9

5. I offered opinions to the doctor [offer_opinions2](#)

Strongly disagree									Strongly agree
0	1	2	3	4	5	6	7	8	9

6. I expressed concerns to the doctor [express_concern2](#)

Strongly disagree									Strongly agree
0	1	2	3	4	5	6	7	8	9

Perceived Efficacy in Interacting with Doctor

Next, I'd like to ask you some questions about your interactions with your doctor.

1. **How confident are you in your ability to know what questions to ask a doctor?** *know_to_ask2*

Not at all confident 0	1	2	3	Very confident 4
---------------------------	---	---	---	---------------------

2. **How confident are you in your ability to get a doctor to answer all of your questions?** *get_answers2*

Not at all confident 0	1	2	3	Very confident 4
---------------------------	---	---	---	---------------------

3. **How confident are you in your ability to make the most of your visit with a doctor?** *maximize_visit2*

Not at all confident 0	1	2	3	Very confident 4
---------------------------	---	---	---	---------------------

4. **How confident are you in your ability to get a doctor to take your health concerns seriously?** *take_serious2*

Not at all confident 0	1	2	3	Very confident 4
---------------------------	---	---	---	---------------------

5. **How confident are you in your ability to get a doctor to do something about your health concerns?** *make_dr_act2*

Not at all confident 0	1	2	3	Very confident 4
---------------------------	---	---	---	---------------------

6. **How confident are you in your ability to ask a doctor questions?** *able_to_ask2*

Not at all confident 0	1	2	3	Very confident 4
---------------------------	---	---	---	---------------------

1-MONTH FOLLOW-UP PATIENT QUESTIONNAIRE

1-Month Follow-up Measures

1. Self-care behaviors (Same measure as at baseline)
2. Self-efficacy related to self-care (Same measure as at baseline)
3. Communication with provider (Same measure as at baseline)
4. Emotional support
5. Tangible support
6. Perceived efficacy in interacting with doctor

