6.2 Secondary Endpoint

Secondary outcomes include: 1) mean score on acceptability checklist; 2) mean score on self-care of heart failure index scores (maintenance, management, and confidence subscales); 3) mean score on caregiver contribution to self-care of heart failure index scores (maintenance, management, and confidence subscales); 4) mean score on perceived efficacy in patient-physician interactions score; 5) mean score on communication with physicians measure

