6.3 Statistical Methods

Analysis for this study will be quantitative pre-post analyses. We will compute descriptive statistics (percentages, means, and standard deviations) for feasibility, acceptability, and behavioral outcomes. For each behavioral outcome (HF self-care behaviors, self-efficacy related to self-care, communication with provider, communication with providers, and perceived efficacy in interactions with doctor), we will use paired t-tests to compare changes in mean scores from baseline to 1-month separately for accompanied patients, companions, and unaccompanied patients. In this pilot study, we are not conducting hypothesis testing. To help plan for future proposals, point estimates of effect sizes for the mean change value in each behavioral outcome will be computed as the ratio of the mean difference in each change value between baseline and 1-month follow-up.

6.4 Sample Size and Power.

This is a pilot study and as such, our sample size was selected based largely on feasibility. Specifically, we examined the expected margin of error for varying recruitment and recruitment yields.

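### Section 6.3 plans a companion baseline to 1-month comparison of communication with provider, but no listed companion measure supplies it

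*Combined protocol and SAP*

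**What the plan says.** **Analysis.** Section 6.3 names the behavioral outcomes: HF self-care behaviors, self-efficacy for self-care, communication with provider (entered twice, singular and plural) and perceived efficacy with the doctor. It applies a paired t-test of baseline to 1-month change to each of them "separately for accompanied patients, companions, and unaccompanied patients". No outcome is excepted for companions.

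**Companion baseline.** The Baseline Administration Protocol in Section 4 says that the companion questionnaire "includes the following measures, which parallel the patient questionnaires", and then lists nine of them.

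**Follow-up.** Section 4.2 introduces a protocol for "administration of the 2 Day Follow Up and the 1 Month Follow Up Calls for each study participant", so companions are to be called at 1 month. The only 1-month list of measures is headed "1-MONTH FOLLOW-UP PATIENT QUESTIONNAIRE", and its third entry begins "Communication with provider (Same measure as at baseline".

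**Endpoints.** Section 6.2 includes "mean score on caregiver contribution to self-care of heart failure index scores" and, separately, a mean score on communication with physicians that is not limited to patients.

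**Accompaniment.** Section 4.1 (Screening/Baseline Visit procedures) lets neither dyad member take part without the other. The baseline questionnaire nevertheless asks patients whether a companion will "come with you to visit your doctor during this study? Variable name: accompanied". A patient who answers no is then asked "Does someone usually go with you to your medical appointments".

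**The concern.** A paired comparison needs the same measure in the same people at both times. For communication with provider in companions, the printed plan shows it at neither time. If the interviews follow the lists, an analysis stated in Section 6.3 will have no data. A baseline that was not asked before the prompt list was used cannot be recovered afterwards, so this should be settled before companions are interviewed.

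The missing companion 1-month list reaches further. The caregiver contribution index is a named secondary outcome, and its change from baseline exists only if it is asked again at 1 month. The documents do not say that it is.

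Two smaller matters sit in the same paragraph of Section 6.3. It analyzes unaccompanied patients although enrolment is by dyad, and it calls the effect size a ratio without saying what the mean change is divided by.

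**Working it through.** The plan gives no figure to reproduce here. The check sets the outcomes in Section 6.3 against the printed lists.

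**Step 1: outcomes.** Section 6.3 has five entries. The two communication entries differ only in singular and plural and are counted as one, which leaves four distinct outcomes. If the second entry was meant for another measure, the documents do not say which.

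**Step 2: lists.** The patient baseline list has 13 measures, with communication with provider as item 10. The companion baseline list has nine: relationship, companion involvement, closeness, HF knowledge, caregiver care behaviors, self-efficacy for patient care, perceived efficacy with the doctor, demographics and health literacy. The patient 1-month list has six.

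**Step 3: cross-check.** Caregiver care behaviors and self-efficacy for patient care are taken as the companion counterparts of the two self-care outcomes. This is an assumption, because the list does not name the caregiver contribution index.

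| Outcome in 6.3 | Patient baseline | Patient 1 month | Companion baseline | Companion 1 month |
|---|---|---|---|---|
| Self-care behaviors | listed | listed | listed (caregiver care behaviors) | no list |
| Self-efficacy for self-care | listed | listed | listed (patient care) | no list |
| Communication with provider | listed | listed | **not listed** | no list |
| Perceived efficacy with doctor | listed | listed | listed | no list |

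Patients: 4 of 4 outcomes at both times. Companions: 3 of 4 at baseline, and 0 of 4 with a printed 1-month measure.

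**Step 4: could another companion measure stand in?**

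- *The 2-day call.* Section 4.2 gives companions measures parallel to the patient 2-day set, which includes a communication scale. That call falls 2 days (±2) after the visit, so it is neither baseline nor 1 month. The patient version is also a different instrument: six agreement items scored 0–9, against three frequency items scored 0–5 at baseline.
- *Perceived efficacy.* This is on the companion baseline list, but Section 6.3 treats it as a separate outcome.
- *The 1-month script.* The 1-month script in Section 4.2 addresses the patient, referring to the visit companion as someone else. The script addressed to the companion refers to an appointment 2–3 days earlier. Neither gives the content of a companion 1-month interview.

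**Step 5: unaccompanied patients.** Under the dyad rule this group is empty unless an enrolled companion does not attend. That can happen: the baseline item allows a no, and the closing baseline script covers a family member who may not come. Section 6.3 does not say whether the group follows the baseline answer or actual attendance, and the two can classify the same patient differently.

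**The case against.** **The lists may understate the instruments.** The printed lists and the reproduced questionnaires do not match perfectly even for patients. The baseline list names companion involvement, but no section has that title. The 2-day list names self-efficacy for self-care, but the reproduced 2-day questionnaire has no such section. Section 5 says that all instruments go to the IRB separately. This stands, and it limits the claim to what is printed. A reader might infer that companions will have no 1-month data, or that no companion change can be computed. The documents do not support that, because 1-month calls are planned for every participant.

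**Section 6.3 may mean each outcome in the groups that have it.** The communication items ask about the respondent's own treatment and illness, so they suit patients. That reading is sensible, but it is not written. Section 6.3 makes no exception, and the objective in Section 2 covers communication in patients and family members together. If that is the intention, one sentence would say so.

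**A stronger reading on patients.** A reader might infer that the separate patient groups cost serious precision and that a pooled all-patient analysis must be the main one. The documents do not support this either. They give no number of unaccompanied patients, and dyad enrolment points to none or few. Section 6.3 names no main estimate, disclaims hypothesis testing, and does not say that its descriptive statistics are split. A patient who attends alone also misses the joint step of the prompt list, so separate analysis is defensible. Nor does Section 6.3 compare accompanied with unaccompanied patients; it looks at change within each group.

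**Conclusion.** The point holds for companions. As listed, one of the four distinct behavioral outcomes, communication with provider, cannot give a companion baseline to 1-month change. For the other three, including the caregiver contribution index, the companion 1-month measure is not stated.

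This rests on three assumptions: that the printed companion baseline list is complete, that the two communication entries in Section 6.3 are one outcome, and that caregiver care behaviors and self-efficacy for patient care represent the caregiver contribution index. If the unprinted companion instruments contain the communication items at both times, only the documentation needs correcting.

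Only secondary outcomes are affected; the primary enrolment outcome is not. The unaccompanied group is a wording conflict between Sections 6.3 and 4.1, with no loss if every companion attends. The missing divisor is a detail to complete. It matters because Section 6.3 gives the planning of future proposals as the purpose of the effect sizes.

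**What to change.** 1. **Companion communication.** Choose one:
   - add the three-item patient measure, reworded for companions, to both the companion baseline and the companion 1-month interview; or
   - remove communication with provider from the companion comparisons in Section 6.3.
2. **Companion 1-month list.** In either case, print the companion 1-month measures in Section 4.2, and state that the caregiver contribution index is repeated.
3. **Unaccompanied patients.** Reconcile this group in Section 6.3 with the dyad rule in Section 4.1. If the group is kept, define it by one named variable: the baseline accompanied item or recorded attendance at the visit.
4. **Effect size.** Name the divisor, for example the SD of change or the baseline SD. Enter communication with provider once.

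**Cost.** Keeping the outcome adds three items to each of two interviews already planned, with no new calls, visits or participants. Removing it gives up one companion comparison. The questions raised in the visit would still be studied through the comparison of audiotapes with prompt lists described in Section 12. The rest is one short list and a few sentences.

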6.5 Interim Analysis. N/A

7 STUDY INTERVENTION (drug, device or other intervention details) N/A- this is not a drug or device trial. Behavioral intervention is described above in Sections 1.1 and 4.2.

8 STUDY INTERVENTION ADMINISTRATION (if applicable) N/A- this is a non-randomized trial design. Behavioral intervention administration is described above in Sections 4.1

9 SAFETY MANAGEMENT

We will not have a DSMC, DsMC, or DMC for this study given that the safety risk to participants is extremely low. However, the PI and Co-I ([name]), both physicians, will review any safety concerns raised, including involving others from the study team (or external to it, if necessary) and decide on an appropriate action. For any unanticipated problems, the PI and study coordinator will conduct an aggregate review using SOP 19.2 and 19.3 to decide if an event or events meets the criteria for unanticipated problems and whether it is an adverse event. If found to meet the requirements, all unanticipated problems will be reported using the online reporting portal within required timelines (SOP 19.5).

10 DATA COLLECTION AND MANAGEMENT

Data will be collected at baseline, the day of the participant's medical appointment, 2 days (+/- 2 days) following the medical appointment and 1 month (+/- 7 days) after the participant's medical appointment. There are several ways in which data may be collected: at baseline, data collection instruments may be administered by telephone or in person using the REDCap online data capture system, the REDCap iPad application, or pen and paper surveys; at the participant's medical appointment, the visit will be audio-recorded; and two day follow up and 1 month follow up data will be collected over the telephone using the REDCap online data capture system, the REDCap iPad application, or pen and paper surveys. All data will be entered into the study REDCap database.

We will have a follow up call with participants 2-days (+/- 2 days) after the visit to gather their perspectives on the utility of the prompt list as well as their perspectives on the communication during the visit and their satisfaction with the visit. The study team will also send participants a reminder letter at least 1 week before time for their 1-month (+/- 7 days) follow-up outcomes assessment. Finally, we will conduct the 1-month follow-up outcomes assessment via phone.

We will make every possible effort to keep the data confidential. All contact information will be kept in electronic files that are password protected and only accessible by study staff. Any hard copy of contact information (used to process the mailing of incentives) will be kept in a secure place (locked office and file cabinet). No names will appear on questionnaires; files linking name with study ID will be kept electronically under password protection. During participant identification, the RAs, PI, and Co-Investigators will know the identity of the patient and their family member. This is required to contact providers for approval, to mail letters to potential patients, and/or to conduct direct in-person recruitment. Upon enrollment, patients and family members will be given a unique study ID number and all data collected thereafter will be linked to this study ID number.

We will use the web-based application known as REDCap (Research Electronic Data Capture project-redcap.org) for data management. REDCap is used for building and managing online surveys and databases. It is a flexible informatics systems-based approach used to support research studies, including clinical trials. Critical components of REDCap include but are not limited to: 1) user authentication and role-based security; 2) intuitive electronic case report forms; 3) real-time data validation, integrity checks and other mechanisms for ensuring data quality (e.g. double-data entry options); 4) data attribution and audit capabilities; 5) protocol document storage and sharing; and 6) central data storage and backups. The graphical view and stats tool allows the user to look at numerical and categorical variables to determine the amount and frequency of missing questionnaire data. The report builder tool serves as a search engine to conduct database queries, which can be used to track attrition rates. The documents linking study identification number to

PHI will be kept on a secure, password-protected server that only the RA/study coordinator and PI can access. Data will be transmitted between the PI and the project biostatistician by copying files directly from one computer to another; email will not be used to transmit data. All computerized data will be kept on password protected computers. Audiotaped data will be stored on a secure, password protected server at UNC-CH. At the end of the award period, the electronic files will be destroyed.

11 RECRUITMENT STRATEGY

11.1 CONSENT PROCESS

Recruitment will be completed by the Study Coordinator or other approved study personnel. Screening to determine eligibility to participate will take place via telephone or in a private location within the clinic. An IRB-approved eligibility form will be used by the RA. The informed consent process will occur in a private location within the clinic.

Potential participants will be given a description of the study in a clear, concise manner and given time to ask questions and have their questions answered by study personnel. Consent will be obtained immediately after the initial consent discussion; and will be obtained directly from the participant. An unsigned hard copy of consent documents (Consent, HIPAA) will be given to each participant for their records. This document will contain contact information for the study coordinator and the PI.

Potential participants (both patient and visit companion) will be given the choice of either reading the consent on their own, or having the consent read to them. If the consent form is read to the participant, the signature page will indicate that the consent was read to the participant. The consent form will describe the study including the potential risks and benefits and will explicitly state that if participants choose not to participate; their medical care at UNC will not be impacted in any way. In addition to the consent form, the HF patient will read a HIPAA authorization form. The patient will be informed that if they choose not to sign the HIPAA authorization form then they may not participate in the study. This information will also be on the written consent form.

The HF patient and the family member will have similar, but separate consent forms. Both the HF patient and the family member will be asked to consent to be audio-taped. The consent form for the family member will state that if s/he is a patient of the health care provider at UNC Hospitals, we will not access their protected health information (PHI) and thus, will not require patient authorization. Potential participants will be allowed to ask questions and have the answers, and the consent forms will then be signed. During this entire process, the PI will be available by pager or cell phone for questions. Copies of all consent documents will be given to participants.

We will also consent select health care providers who see patients at the Cardiology clinic at Meadowmont. Most, if not all, of these providers are individuals who consented and participated in the PI's previous study. The health care providers will be approached by the PI or Co-I ([name]) either in person or via email, informed of the study, and asked to participate. The informed consent process will occur in a private location within the Cardiology clinic. An IRB-approved written consent form will be given to the health care provider to read while the RA explains the form to them. The consent form for the health care provider will state that taking part in this research is not a part of their University duties as an employee, and refusing will not affect their employment at UNC-CH. In addition, the consent form will also state that the health care provider will not be offered or receive any special job-related consideration if they choose to take part in

this research. Potential participants will be allowed to ask questions and have them answered, and the consent forms will then be signed. During this entire process, the PI will be available by pager or cell phone for questions. Copies of all consent documents will be given to participants.

All consent forms will be designed to be read at the 5th grade level. They will describe the study, its potential benefits and risks, and indicate that participation is strictly voluntary and that participants may stop at any time.

